Once recruited to the study and after baseline measures are taken at T0 by the study coordinator, the randomization will be performed. Since study groups will be subdivided by gender, separate randomization will be performed for males and females. Block randomization will be used. Based on gender, 20 opaque envelopes will be generated containing the group allocation (10 for the vibration study group, 10 for the non-vibration control group). At the time of randomization, the

subject will choose an envelope and disclose the group assignment. For subjects allocated to the vibration group, the study coordinator will provide detailed instructions as to how to operate the appliance and will instruct those subjects to use it for 20 minutes per day.

Timetable of Study Assessments

Assessment/ Visit	Screen	Baseline T0	Visit T1	Visit T2	Visit T3
Week	2d-to -6w	0	5-6	10-12	15-17
Consent	X				
Inclusion Criteria/ Confirm	X	X			
Alginate Impression		X	X	X	X
Randomization *		X			
Braces applied /bonded		X			
Vibration Appliance instructions**		X			
Saliva Collection		X	X	X	X
Clinical Data		X	X	X	X
Periotest		X	X	X	X
Pain Diary*** & OHIP 14		X	X	X	X***
Model Analysis		X	X	X	X
Record Adverse Effects		X	X	X	X

*Randomization before bonding

**For vibration group only- SC initially provides device and manufacturer's instructions.

*** Diary provided @ Baseline & visit T1, T1 to be collected on next visit.

III. Data Collection Procedures (See Study Timetable)

On the day of bonding (T0), prior to the placement of any appliances, baseline unstimulated whole saliva will be collected and Periotest will be performed on selected teeth in the mandibular arch. In addition, alginate model impressions will be taken. These procedures will be described in more detail in the next sections. Once baseline measures have been taken, the PI will perform the randomization and notify the study coordinator as to which group the subject is assigned to ("vibration treatment" or "no vibration"). The patients allocated to the vibration treatment group

will be provided with the AcceleDent appliance and instructed to use the 20 minutes per day according to the manufacturer's instructions.

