After fixed appliances are placed and tooth movement begins, subjects will proceed with standard orthodontic treatment with or without vibration treatment based on allocation. Collection of saliva samples, Periotest and alginate impressions will be taken at T1 (5-6 weeks post-T0), T2 (10-12 weeks post-T0) and T3 (15-17 weeks post-T0). Subjects will be seen between noon and 5pm to help minimize possible confounding of salivary markers by circadian rhythms.

Salivary Biomarkers

Collection of unstimulated whole saliva will be performed using the same methods described by Navazesh and Kumar⁴⁸:

"The patient is advised to refrain from intake of any food or beverage (water exempted) one hour before the test session. Smoking, chewing gum and intake of coffee also are prohibited during this hour. The subject is advised to rinse his or her mouth several times with deionized (distilled) water and then to relax for five minutes.

The patient is then told the following: "I will first obtain measures of saliva flow while you are at rest. This means that before and during the collection you should make every effort to minimize movement, particularly movements of your mouth. To begin a collection trial, I will ask you to swallow to void the mouth of saliva. Then you should lean your head forward over the test tube and funnel" (demonstrate). "Keep your mouth slightly open and allow saliva to drain into the tube. Keep your eyes open. At the end of the collection period, I will ask you to collect any remaining saliva in your mouth and spit it into the test tube. This movement should be done very quickly and should be done in the same manner from trial to trial. This is very important. Do you understand the procedures?"

When you start a trial, tell the subject:

1. *Swallow to begin a trial (begin timing).*
2. *Make as little movement as possible. Do not swallow, and keep your eyes open during collection periods.*
3. *At the conclusion of the trial, collect the remaining saliva and spit it out."*

Unstimulated whole saliva will be collected by passive drooling into sterile centrifuge tubes on ice for 15 minutes or once 2-10mL of saliva is collected at baseline and each visit, whichever occurs

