(the study coordinator) will collect all tooth mobility measurements with the Periotest and means will be evaluated using non-parametric statistical analyses.

A Wilcoxon Rank Sum test for independent samples will be used to assess differences between groups for all the continuous variables with an $\alpha=0.05$ for irregularity index changes-Periotest measurements, VAS & OHIP-14 measures.

Salivary biomarker expression will be analyzed by ANOVA to assess differences between the four study groups at each time point. The study coordinator and principal investigator will perform statistical analyses.

VII. Timetable Table Timeline of Performance Goals:

Activity	Year 1-2014			Year 2-2015		
	X					
IRB, Staff training & preparation	X					
Subject Recruitment & Enrollment	X	X	X			
Final Assessments/Endpoints (17 weeks)				X		
Data Entry & Cleaning				X	X	X
Data analyses					X	X
Report writing						X

Expected Start Date: 2/1/2014

General Time Table

January 2014

Submit IRB for full board review

February 2014

Enrollment begins

Begin data collection for T0 time point in recruited subjects

August 2014

Initially recruited subjects complete study to final endpoint (T4)

June 2015

All consented subjects will have completed study

Data collection complete (N=20)

July 2015

Data analyses conducted

August 2015

Manuscript Preparation

➤ ***Expected Completion Date:*** August 2015

5) **Budget**

Patients will be responsible for covering the cost of orthodontic treatment in the University of Connecticut Orthodontics Clinic (either directly or with insurance). However, a deduction of \$400.00 on the standard orthodontic fees will be given to every patient enrolling in the research. The participants will receive this incentive in the form of \$100.00 at each research appointment completed until the maximum benefit is reached. If a participant is not compliant with the study protocol, he/she will be dismissed from the study and will not receive any further compensation. The same orthodontic procedures will be used for all subjects in this study regardless of study group.

Please see the attached budget detailing the study-specific costs.

6) **Dissemination**

The results of this research will be published in a peer-reviewed dental journal. In addition, this work is likely to be presented at national/international meetings.

References

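### The only Periotest reader knows each subject's arm, so the tooth-mobility readings at T1 to T3 are unmasked

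*Combined protocol and SAP*

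**What the plan says.** Tooth mobility is a secondary outcome (Outcome Assessments). Hypothesis 2 predicts that it is higher with vibration plus fixed appliances than with fixed appliances alone.

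- **Who reads.** Section VI assigns all readings to one calibrated examiner: "the study coordinator) will collect all tooth mobility measurements with the Periotest".
- **Who learns the arm.** Section III says that "the PI will perform the randomization and notify the study coordinator as to which group the subject is assigned to".
- **Who handles the device.** Section II says that, for the vibration arm, "the study coordinator will provide detailed instructions as to how to operate the appliance". The timetable footnote agrees: "For vibration group only- SC initially provides device".
- **Envelope.** Section II says the "subject will choose an envelope and disclose the group assignment", without saying to whom or who is present.
- **Timing.** Section II says that "after baseline measures are taken at T0 by the study coordinator, the randomization will be performed". Section III then schedules the later readings: "Collection of saliva samples, Periotest and alginate impressions will be taken at T1", and again at T2 and T3.
- **Measurement controls.** Periotest Measurement Procedures names the teeth and requires archwire removal, a 2 mm tip distance, a perpendicular angle and triplicate readings with means recorded. The examiner chooses a contact site that leaves room for the tip and allows consistent readings.
- **Masking elsewhere.** Dental Model Analysis uses two blinded evaluators for the casts. No section masks the Periotest reader.

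**The concern.** The reader knows both the arm and the direction the trial expects. The Periotest gives a number, but a person holds the handpiece and picks the site. If site choice or handling drifted with knowledge of the arm, the shift would run the same way through all three repeat readings, so averaging them would not cancel it. With one reader there is no second set of readings to expose it, and section VI plans rater-reliability checks only for the irregularity measurements. Such a shift could not be separated from a treatment effect afterwards. What is at stake is the credibility of the answer to Hypothesis 2, not the trial's primary outcome.

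**Working it through.** **Step 1: trace what the coordinator knows at each reading.**

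| Reading | Position relative to allocation | Arm known to the reader? |
|---|---|---|
| T0 | before randomization (section II) | No |
| T1, T2, T3 | after randomization | Yes |

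Two routes are explicit: notification by the PI (section III), and giving the device and instructions to the vibration arm (section II and timetable footnote). Either is enough. Envelope opening is a possible third route, but the text does not settle who is present. The protocol never calls the Periotest unmasked; that follows from the two explicit routes.

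**Step 2: ask whether the stated controls hide the arm.** Numeric output, fixed distance and angle, named teeth, triplicates, calibration and the call for consistent readings all limit random error and the room for discretion. None conceals allocation.

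**Step 3: illustrate what an arm-related shift would do.** The plan states no Periotest power, SD, effect size or bias figure, so there is nothing to reproduce. The shifts below are assumptions.

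Inputs from the plan: a Wilcoxon rank-sum test at α = 0.05 (section VI) and 40 subjects in four gender-by-arm groups (section IV), hence 10 per group and 10 + 10 = 20 per arm. Because "separate randomization will be performed for males and females" and section VI does not define the groups for this test, both sizes are shown. Sidedness is not stated; two-sided is assumed. An assumed 20% disqualified gives 20 × 0.8 = 16 and 10 × 0.8 = 8.

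Model: no true effect; vibration values ~ N(b, 1), control values ~ N(0, 1). Here b is the observer shift in SDs of whatever per-subject value is compared at one visit; section VI does not say whether that is one tooth, a mean over teeth or a change from T0. Each cell uses 100,000 simulated trials with exact critical values. Entries are two-sided rejection rates (%).

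| Per arm | b = 0 | 0.1 | 0.2 | 0.3 | 0.5 |
|---|---|---|---|---|---|
| 20 | 5.0 | 6.1 | 9.1 | 14.5 | 32.1 |
| 16 | 4.7 | 5.5 | 7.9 | 11.8 | 25.8 |
| 10 | 4.3 | 4.8 | 6.2 | 8.4 | 16.1 |
| 8 | 4.9 | 5.3 | 6.5 | 8.3 | 15.0 |

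The exact null sizes are 4.91%, 4.68%, 4.33% and 4.99% for 20, 16, 10 and 8 per arm, so the b = 0 column is as expected.

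Check by normal approximation: rate = Φ(b/√(2/n) − 1.96) + Φ(−b/√(2/n) − 1.96). For n = 20 and b = 0.3, √(2/20) = 0.316 and 0.3/0.316 = 0.949, so the rate is Φ(−1.011) + Φ(−2.909) ≈ 0.156 + 0.002 = 15.8%. This is a little above the rank-sum figure, as expected of a test on means with normal data.

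If the test were one-sided in the hypothesized direction, shifts of 0.1 / 0.2 / 0.3 / 0.5 SD would give 8.9 / 14.6 / 22.6 / 44.1% with 20 per arm and 6.9 / 10.0 / 14.1 / 25.7% with 10 per arm.

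**The case against.** The strongest reply is that the weight is small and the benefit unproven. This is one secondary outcome in a 40-subject pilot, read by a device in triplicate under positioning rules, and nothing shows that bias occurs. The percentages come from assumed shifts and say nothing about this trial. Subjects know their arm, no sham is described, and the same coordinator meets them at every visit, so masking will leak, and a leak at T1 carries over to T2 and T3. The OHIP-14, given at the same visits, could also prompt talk about the device. The added PI work goes beyond T0, because device questions would go to the PI throughout follow-up.

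Much of this stands. The bias size cannot be derived, nor can the amount by which the fix would lower it; the table shows sensitivity and is not evidence of harm. Masking would be partial, and later device questions are a real if modest addition to PI time. The OHIP-14 risk is smaller than it looks, since its items ask only about teeth and mouth, and it can simply follow the Periotest.

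None of this masks the reader. Occasional, recorded unblinding is better than knowledge of every subject's arm by design, and the protocol already accepts the principle by blinding the cast evaluators.

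**Conclusion.** The concern holds. As written, the sole Periotest reader knows the allocation for every T1, T2 and T3 reading, and no other section repairs this. The magnitude is unknown. Under assumed shifts of 0.1 to 0.5 SD, the two-sided false-positive rate runs from about 6% to 32% with 20 per arm and from about 5% to 16% with 10 per arm, close to nominal at the low end. These figures rest on normal data with equal SDs and no true effect.

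The change should be made, but it is not critical: mobility is secondary, the trial is a pilot, and the salivary ELISA results and cast readings are untouched. The argument for acting is that the fix is cheap and the bias, if present, could not be removed later.

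**What to change.** **Allocation and device**

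1. Section II: state that the envelope is opened with the PI only.
2. Section III: delete the part of the randomization sentence that has the PI notify the coordinator.
3. Section II and the timetable footnote: have the PI provide the device and the instructions.

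**Visits T1 to T3**

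4. Fix the order. Keep saliva first, since its collection method asks for minimal mouth movement beforehand. The coordinator then takes the Periotest before diaries are collected, the OHIP-14 is given, adverse effects are recorded or the device is discussed. Section III already lists saliva before Periotest but sets no sequence within a visit.
5. Ask subjects not to mention their group, send device questions to the PI, and log any unblinding by subject and visit.
6. Withhold arm codes from the coordinator, who is also a named analyst, until the Periotest data are locked.

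**Cost.** Protocol wording, plus about 20 short instruction sessions (10 male and 10 female vibration subjects) moved to the PI, who already randomizes and takes no Periotest readings. Later device questions, an unblinding log and custody of the codes come on top. No new staff, visit or measurement is needed.

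**Limits.** Some unblinding will remain, because subjects know their arm and the coordinator still confirms appointments and collects diaries. The fix also assumes that the device is used away from the visit, which is inferred from the daily-use instruction.

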Studies have shown that the oral health quality of life (OHQoL) is impacted by orthodontic treatment. After orthodontic treatment, studies have shown a significant improvement in OHQoL compared to baseline measures.^{44,45} However, during orthodontic treatment, OHQoL reduces significantly, as has been shown in younger patients.⁴⁶ Motivation measures related to self-empowerment and participation in treatment have been shown to improve the overall OHQoL in schoolchildren.⁴⁷ Limited studies are available regarding the OHQoL during orthodontic treatment and further studies are needed to determine which factors contribute to improving the overall experience for patients successfully completing orthodontic nonextraction treatment with tooth movement .

Study Rationale

Currently, orthodontic treatment typically lasts approximately 2 years. There are a number of advantages for reducing the duration of treatment, including reducing the potential risk of caries², root resorption³ and for minimizing patient “burn out” from prolonged treatment.

While some evidence does exist that vibration may accelerate the speed of tooth movement, the biological mechanism is still unknown. Identification of specific factors involved in tooth movement that are further stimulated by vibration would help to understand the mechanisms involved as well as discover possible biologic targets which could be utilized or modified to maximize the benefits of vibration treatment.

The purpose of this study is to identify novel biological factors that are expressed in patients undergoing orthodontic tooth movement in conjunction with vibration appliance therapy.

Outcome Assessments

- *Primary outcome:* Changes in the expression of salivary biomarkers of bone remodeling
- *Secondary outcomes:* Changes in 1) tooth mobility, 2) change in alignment 3) changes in pain and OHQoL

Hypotheses, aims and objectives

Scientific Hypotheses

- 1) The expression of biological markers of bone remodeling are increased in combined vibration-fixed appliance treatment.
- 2) The degree of tooth mobility is increased in patients undergoing combined vibration-fixed appliance treatment compared to orthodontic treatment alone.
- 3) The percent change in alignment is greater in patients undergoing combined vibration-fixed appliance treatment compared to controls during the first 6 months of treatment.

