first⁴⁹. Once saliva is collected, samples will be kept on ice and supplemented with proteinase inhibitor. Samples will then be centrifuged for 10 minutes at 3000 rpm to remove cellular debris and supernatants will be collected and stored at -80°C until they are ready to be analyzed for biomarkers⁵⁰.

Biomarkers will be evaluated by ELISA assay by a direct sandwich method using a standard protocol. Primary antibodies to selected factors will be pre-coated onto 96 well dishes. Sample product or standards will be incubated on the coated plates and a secondary conjugated antibody will be used to detect binding using chemiluminescence. Selected target biomarker antibodies include ALP, RANKL/TRANCE, OPG, Osteocalcin (marker of bone formation), MMP8, MMP13, TNF α , IL1a, IL1b, IL3, IL6, IL11 and IL18. Human antibodies to these targets will be obtained from R&D Systems, Inc. In addition, salivary C-terminal telopeptide of type I collagen (CTX) (an indicator of bone resorption) will be analyzed by ELISA assay using a RatLaps kit (Immunodiagnosis System, Inc.)

Periotest Measurement Procedures

This measurement is obtained at baseline and each visit. The degree of tooth mobility will be used using a Periotest device (Siemens AG, Bensheim, Germany) on the central incisors, canines and 2nd premolars in both mandibular quadrants as previously described by Liou *et al.*⁵¹ The archwire will be removed and the Periotest measurements will be taken in triplicate, with means recorded. The Periotest handpiece will be positioned such that the tip is 2mm from the labial surface and perpendicular to the tooth surface for measurements. The examiner will locate an area on the labial surface that has sufficient space for the tip to contact the tooth surface and be able to take consistent measurements. Detectable Periotest values (PTV) range from -8.0 to +50, with data values correlated, as below, to the degree of mobility based on Miller's index^{52,53}.

PTV Measure	Indication
-8.0 to +9.0	No movement distinguishable
+10.0 to +19.0	First distinguishable sign of mobility
+20.0 to +29.0	Crown deviates within 1mm of normal position
+30.0 to +50.0	Mobility is easily noticeable

Dental Model Analysis

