Two blinded clinical evaluators will assess the rate of alignment of the lower incisors for both groups. Analyses of dental casts will be done on the mandibular cast using a method based on Little's irregularity index. Little's irregularity index was developed to assess amount of anterior tooth displacement from canine to canine (see Cast Irregularity Data Collection Form). Contact displacement will be measured in millimeters around the arch from canine to canine. Irregularity will be measured on models from each of the four time points and be evaluated based on percentage change over the 6-month evaluation period.

Orthodontic Pain Assessment

Subjects will be given a pain diary on the baseline (T0), visits T1 & T2 to record the level of orthodontic pain each evening for the first 7 days after each study visit. The degree of pain will be assessed using a Visual Analog Scale (VAS) ranging from 1 (least pain) to 10 (highest pain)⁵⁴. In addition, patients will report if the pain is constant or only present on biting/chewing⁵⁵. The subjects will return the completed diary to the next visit to be collected by the study coordinator and kept in the study record.

Oral Health Quality of Life (OHQoL)

To assess the impact of the vibration appliance on the overall oral health quality of life of the subject, subjects will be given an Oral Health Impact Profile (OHIP-14) questionnaire⁵⁶. The OHIP-14 consists of 14 questions divided into specific dimensions including functional limitation, physical pain, psychological discomfort, physical disability, psychological and social disability and overall life handicap from orthodontic treatment with or without the vibration appliance. The OHIP-14 (exhibit below) will be administered at each study visit and the profile changes will be compared across time points in data analyses.

OHIP-14 Questionnaire:

Dimension	Question	Weight
Functional Limitation	Have you had trouble pronouncing any words because of problems with your teeth or mouth?	0.51
	Have you felt that your sense of taste has worsened because of problems with your teeth or mouth?	0.49
Physical Pain	Have you had painful aching in your mouth?	0.34
	Have you found it uncomfortable to eat any foods because of problems with your teeth or mouth?	0.66
Psychological Discomfort	Have you been self-conscious because of your teeth or mouth?	0.45

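### The rank-sum test for the secondary outcomes leaves out the sex strata and uses T0 at most as a change score, which gives up some power; for Periotest and OHIP-14 the analysed value is not fixed

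*Combined protocol and SAP*

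**What the plan says.** Section VI (Statistical/Data Analysis) gives one sentence to the secondary outcomes: "A Wilcoxon Rank Sum test for independent samples will be used to assess differences between groups for all the continuous variables", at alpha 0.05, "for irregularity index changes-Periotest measurements, VAS & OHIP-14 measures". It names no covariate or stratum and does not say whether the test is two-sided.

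On sex, section II (Randomization Procedures) says "separate randomization will be performed for males and females", with 10 vibration and 10 control envelopes for each sex. The biomarker ANOVA in section VI compares the four sex-by-treatment groups, so sex is represented there.

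On T0, the text differs by outcome:

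- Outcome Assessments lists the secondary outcomes as "Changes in 1) tooth mobility, 2) change in alignment 3) changes in pain and OHQoL".
- Irregularity (Dental Model Analysis) will "be evaluated based on percentage change over the 6-month evaluation period".
- Periotest: "This measurement is obtained at baseline and each visit". Section VI refers to measurements, not changes.
- OHIP-14 "will be administered at each study visit and the profile changes will be compared across time points in data analyses", with no method attached. Section VI refers to measures.
- Pain is scored in a diary handed out at the visit, "to record the level of orthodontic pain each evening for the first 7 days after each study visit". No score before bonding is described.

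**The concern.** The design balances the arms on sex and pays to measure T0 on three of the four secondary outcomes, but the planned test makes little use of either. If sex or T0 predicts the later value, that variation stays in the noise. A raw follow-up value makes no use of T0. A simple change score subtracts all of T0, which over-corrects when the correlation between T0 and follow-up is low. Which of the two does better depends on a correlation that nobody knows in advance, and for Periotest and OHIP-14 the text lets the analyst pick after seeing the data.

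Hypotheses 2 to 4 (mobility, alignment, pain) all rest on this test with 20 per arm. At that size a chance T0 difference of more than 0.3 SD is not rare: its standard error is √(2/20) = 0.316 SD, and 0.3/0.316 = 0.95 gives a two-sided probability of about 34% per outcome.

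**Working it through.** **1. Inputs from the documents.** Allocation is 2 sexes × (10 + 10) = 40, or 20 per arm, which matches the stated total. There is no effect size, SD, power, T0 correlation or sex effect, so there is no power figure to reproduce.

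**2. Assumed inputs.** T0-to-follow-up correlation ρ of 0.3 to 0.7 (extended to 0.9), normal data, two-sided alpha 0.05, no dropout. The true effect is 0.7 SD with a sex effect of 0.5 SD; as a cross-check, 0.8 SD with no sex effect.

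**3. Closed form.** The variance factor v is 1 for the raw follow-up value, 2(1 − ρ) for change and 1 − ρ² for ANCOVA on T0. The effect detectable with 80% power is (1.960 + 0.842) × √[(2/20) × v/e], where e = 3/π = 0.955 for rank-sum and 1 for ordinary ANCOVA.

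| ρ | Rank-sum, raw | Rank-sum, change | ANCOVA |
|---|---|---|---|
| 0.3 | 0.91 SD | 1.07 SD | 0.85 SD |
| 0.5 | 0.91 SD | 0.91 SD | 0.77 SD |
| 0.7 | 0.91 SD | 0.70 SD | 0.63 SD |

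The ANCOVA factor never exceeds either of the others. Its ratio to the change factor is (1 − ρ²)/[2(1 − ρ)] = (1 + ρ)/2: 0.65, 0.75 and 0.85 at ρ = 0.3, 0.5 and 0.7, and 0.90 and 0.95 at 0.8 and 0.9. The advantage over change therefore shrinks as ρ rises.

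**4. Simulated power, 0.7 SD effect** (3,000 trials per row, 10 males and 10 females per arm; rank ANCOVA of the follow-up value on arm, ranked T0 and sex).

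| ρ | Rank-sum, change | Rank-sum, raw | Rank ANCOVA | Gain over change | Gain over raw |
|---|---|---|---|---|---|
| 0.3 | 0.41 | 0.53 | 0.57 | 16 points | 4 points |
| 0.5 | 0.57 | 0.54 | 0.67 | 10 points | 13 points |
| 0.7 | 0.77 | 0.55 | 0.81 | 4 points | 26 points |

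Repeat runs moved single powers by up to about 3 points; in one, rank ANCOVA gave 0.58, 0.65 and 0.79 against about 0.43, 0.55 and 0.77 on change. I carry forward about 3 to 15 points over change and about 4 to 26 over raw values. At ρ = 0.8 and 0.9 (4,000 trials), rank-sum on change gave 0.92 and 0.996 against 0.91 and 0.990 for rank ANCOVA, so no gain remains.

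**5. Cross-check, 0.8 SD effect, no sex effect.** Raw / change / rank ANCOVA: 67/53/70% at ρ = 0.3, 67/67/77% at 0.5 and 67/87/90% at 0.7. The pattern is the same.

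**6. Irregularity as percentage change.** Assuming a T0 mean of 8 mm, a follow-up mean of 4 mm and an SD of 2 mm, rank-sum on percentage change gave 0.55, 0.65 and 0.76 at ρ = 0.3, 0.5 and 0.7. Rank ANCOVA of the follow-up value gave 0.58, 0.65 and 0.79, a gain of 3, 0 and 3 points (up to about 4 without a sex effect at T0). A check with ranked percentage change as the response gave gains of similar size over this range.

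**7. Pain (sex only, 0.8 SD effect).** If sex explains 0, 10 or 20% of the variance, the unstratified test has 67, 63 or 57% power. The sex-stratified (van Elteren) test has about 66% throughout: −1, +3 or +9 points.

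**8. Type I error.** With no treatment effect, rank-sum on raw values rejects about 5% of the time if sex does not matter, about 4% if sex explains 10% of variance and 2.5 to 3% if it explains 20%. On change scores it stays near 5%. Rank ANCOVA gave 4.4 to 5.6%.

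**The case against.** The strongest reply is that the plan does use T0. Irregularity is a percentage change, every secondary outcome is defined as a change, and OHIP-14 profile changes are to be compared. A reader might infer that the test ignores T0 altogether; the documents do not support that. The claim could be true of Periotest, and of OHIP-14 if visit values are tested, but it is wrong for irregularity and does not apply to pain, which has no pre-bonding score. Nor do all three hypotheses lose power through T0: pain can gain only from sex, and alignment gains little.

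Second, every power figure rests on assumed inputs. That stands. No document shows that sex predicts these outcomes, and stratifying a change score adds nothing when the sex shift is the same at both visits (67% against 67% at ρ = 0.5).

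Third, this is a self-described pilot that claims no power, and a simple valid test is defensible. That also stands and limits the weight of the point. It does not settle which value is tested for Periotest and OHIP-14.

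Fourth, rank ANCOVA gives a difference in ranks, not in millimetres or score points, and replacing percentage change by the follow-up value would change the stated alignment endpoint. Both objections are right, and the fix allows for them.

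**Conclusion.** The point holds as one of efficiency and prespecification. The planned test omits the sex strata, never uses T0 as a covariate, and leaves the analysed value open for Periotest and OHIP-14. A reader might take the omission of the strata as a source of false positives. The calculations show the opposite: the test is valid and, when sex is prognostic, conservative on raw values.

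The gain matters most for Periotest and OHIP-14, is small for irregularity, and for pain depends wholly on whether sex is prognostic. It assumes a 0.7 SD effect (0.8 SD for pain), 20 per arm and no dropout. The statement that the gain vanishes at correlations of 0.8 and above applies to simple change only; percentage change was assessed at 0.3 to 0.7. The General Time Table gives 20 subjects at the end of data collection, against 40 elsewhere. That needs reconciling, because all powers would be lower with 10 per arm.

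**What to change.** State for each outcome the value analysed, the visit and the model:

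- **Periotest and OHIP-14:** compare arms at T3, with T1 and T2 supportive, by rank ANCOVA of the visit value on arm, with ranked T0 and sex as covariates. State that the T0 OHIP-14 is completed before allocation is disclosed; the list of procedures before randomisation does not name it.
- **Irregularity:** keep percentage change as the endpoint, rank it, and adjust for ranked T0 irregularity and sex.
- **Diary VAS:** use a van Elteren test stratified by sex on a per-visit summary such as the 7-day mean.
- **Reporting:** take the p-value from the adjusted rank analysis. Give the effect in original units with a 95% confidence interval from an ordinary ANCOVA on T0 and sex (bootstrap interval if skewed), or a sex-stratified Hodges-Lehmann shift for VAS. State that tests are two-sided, if that is intended.

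The cost is SAP wording and slightly more analysis work, with no new data. About 1 point of power is lost for VAS if sex is not prognostic. The p-value and interval come from different models and may occasionally disagree, so the SAP should say which governs.
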